**3) IRB Review History**

The IRB reviewed the protocol and requested that the FDA determines whether an IND is needed or exempt.

**4) Objectives**

a) To determine the efficacy of photodynamic therapy (PDT) in the treatment of seborrheic dermatitis.

b) To determine how PDT alters the skin microbiome in subjects with seborrheic dermatitis before and after treatment.

c) To determine how PDT alters sebum secretion rates in subjects with seborrheic dermatitis before and after treatment.

We hypothesize that PDT will be efficacious in the treatment of seborrheic dermatitis.

**5) Background**

Seborrheic dermatitis is a common chronic inflammatory disorder with a prevalence estimated at 3-5% [1, 2]. Although the exact pathophysiology is unclear, seborrheic dermatitis is more prevalent in individuals that are more heavily colonized with the *Malassezia spp* fungal organism, those with more residual sebum (for example in neuropathic patients such as in Parkinson's disease), and in those with higher sebum production, which leads to more lipid byproduct build up [2]. Current topical treatments include the use of topical antifungals, topical steroids, and topical calcineurin inhibitors [3, 4]. The success of topical treatments requires long-term use and depends on the compliance of the patient. Furthermore, these treatments can expose patients to potential side effects such as atrophy, thinning of the skin and telangiectasias in response to topical steroids. Therefore, alternative therapies that provide long-term control are needed.

This pilot project investigates the use of PDT may be useful in the treatment of seborrheic dermatitis based on the following: 1) The *Malassezia spp* is capable of forming biofilms [5], 2) PDT has been shown to be effective against *Malassezia spp* [6, 7], 3) PDT can break up biofilms of both bacterial and fungal origin [8], and 4)

PROTOCOL TITLE: Pilot study for the use of photodynamic therapy in the treatment of seborrheic dermatitis

benzoyl peroxide, a prooxidant treatment similar to PDT, has been shown to be effective in the treatment of seborrheic dermatitis [9].

**6) Inclusion and Exclusion Criteria**

Healthy subjects 18 years or older with seborrheic dermatitis of the face will be included.

Subjects who are taking systemic corticosteroids (at doses of prednisone greater than or equal to 5 mg daily) or antibiotics (PO, IM or IV) will have to undergo a 4 week “wash-out” period before participating in the study. Subjects who are using topical anti-fungals, steroids, antibiotics, permethrin, or calcineurin inhibitors will have to wait 2-weeks before enrolling. Washout will only occur if subject signs this consent form and the prescribing physician advises for a washout following consultation. Women who have started new birth control regimens within the last two months will have to wait until two months after the start of their regimen.

Recruited subjects will be permitted to use bland emollients, but they will be instructed to refrain from using topical emollients such as PromiseSeb® which have been clinically studied for the treatment of seborrheic dermatitis. The exclusion criteria will also include the presence of other untreated inflammatory conditions (such as lupus, atopic dermatitis, or psoriasis) or untreated malignancies on the face (including skin cancers such as basal cell carcinoma, squamous cell carcinoma and melanoma).

Any subjects with known or suspected hypersensitivity to any constituent of the study medication or a history of photosensitivity due to conditions such as lupus erythematosus and porphyria will be excluded. Subjects who have had photodynamic therapy (PDT) to the face for any reason within the past year will be excluded as well.

Adults unable to consent, individuals under the age of 18, pregnant or breastfeeding women and prisoners will be excluded from the study.

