## **12) Procedures Involved**

Duration of seborrheic dermatitis, previous treatments for seborrheic dermatitis and patient response to the treatments will be recorded. Facial photography will be done for grading the Seborrhea Area and Severity Index Face (SASI-F). All seborrheic dermatitis patients will be graded using the SASI-F [3]. This score is a composite score as follows: the area index, also known as the relative area of facial involvement, is denoted as a fraction of 1 with the normal hairline defining the boundaries of the face. Erythema and scale are separately scored on a 5-point scale using the definitions used to conduct Psoriasis Area and Severity Index scoring (ie, 0 = none, 1 = slight, 2 = moderate, 3 = striking, and 4 = exceptionally striking).

The scores for erythema and scale are then summed and multiplied by the relative area of facial involvement ratio. The maximal score is 8 whereas no involvement would have a score of 0. The inclusion criteria will be similar to the previous trial that used the SASI-F in their analysis [3]. This study will consist of subjects with an erythema score of at least one with the presence of at an area index of 5% or more.

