## **32) Consent Process**

Written consent will be obtained from patients at the UC Davis outpatient Dermatology clinic in Sacramento. We will be following the SOP: Informed Consent Process for Research. After obtaining consent, there will be a two-week waiting period before initiating treatment so that the patient may begin using only

PROTOCOL TITLE: Pilot study for the use of photodynamic therapy in the treatment of seborrheic dermatitis

Dove soap and stop using any other products to their face. If the patient is using systemic treatment they will have to wait 4 weeks before participating, and if the patient is using topical treatment they will have to wait 2 weeks before participating. Patient will also be provided a moisturizer and sunscreen to use as needed. Patient will be encouraged to use sunscreen following PDT treatments.

Only English-speaking, adult subjects who are not cognitively impaired and are able to consent will be recruited.

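### Other facial inflammatory disease is excluded only if untreated, yet the wash-out and run-in stop its facial treatment, so a second red or scaly disease could return and be counted by SASI-F

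*Combined protocol and SAP*

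**What the plan says.** **Eligibility.** Section 6 (Inclusion and Exclusion Criteria): "The exclusion criteria will also include the presence of other untreated inflammatory conditions (such as lupus, atopic dermatitis, or psoriasis"). The same sentence goes on to untreated malignancies on the face. Treated inflammatory disease is not mentioned.

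**Wash-out.** Also in section 6: "Subjects who are using topical anti-fungals, steroids, antibiotics, permethrin, or calcineurin inhibitors will have to wait 2-weeks before enrolling". Users of systemic corticosteroids (prednisone 5 mg daily or more) or systemic antibiotics "will have to undergo a 4 week “wash-out” period before participating in the study". A condition applies: "Washout will only occur if subject signs this consent form and the prescribing physician advises for a washout following consultation".

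**Run-in.** Section 32 (Consent Process) sets a two-week wait between consent and treatment, in which the subject is to use only "Dove soap and stop using any other products to their face". It also says: "If the patient is using systemic treatment they will have to wait 4 weeks before participating", without limiting this to a drug class.

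**Outcome.** Section 12 (Procedures Involved): "Erythema and scale are separately scored on a 5-point scale using the definitions used to conduct Psoriasis Area and Severity Index scoring". The two scores are added and multiplied by the fraction of the face involved. On entry severity, with 5% as the minimum area: "This study will consist of subjects with an erythema score of at least one with the presence of at an area index of 5% or". Grading is blinded and uses calibrated photographs. Section 14 (Data Management) takes complete clearance of the seborrheic dermatitis, compared within the individual, as the primary endpoint.

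**The concern.** Psoriasis and atopic dermatitis of the face are commonly controlled with topical steroids or calcineurin inhibitors, and both classes are on the wash-out list. A subject whose second disease is controlled in this way is not *untreated* at consent, so the exclusion does not catch them on its wording. The trial's own procedures then remove the treatment that made the subject eligible.

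If the second disease returns, SASI-F counts its erythema and scale together with those of the seborrheic dermatitis. What is at stake is whether the score and the clearance endpoint still describe the disease under study. With 12 subjects, one or two such cases matter.

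**Working it through.** The plan derives no figure here, since section 14 declines a power analysis. The main check is therefore to set the sections side by side. The arithmetic after it is illustration.

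**1. Can such a subject enter?**
- Section 6 excludes *untreated* disease only, so treated disease is not excluded.
- Section 6 requires two weeks off topical steroids and calcineurin inhibitors, and section 32 stops other facial products. Any such subject who enters has stopped facial treatment.
- No section says at which point *untreated* is judged, and none requires a check for other dermatoses after the wash-out.
- For systemic drugs, section 6 names corticosteroids and antibiotics only, whereas section 32 refers to systemic treatment in general. Whether other systemic therapy is stopped depends on which wording governs. The two sections must be reconciled.

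**2. Would the score count the second disease?**
SASI-F = (erythema + scale) × area fraction. A patch of second disease at the entry thresholds, with erythema 1, scale 0 and area 0.05, gives (1 + 0) × 0.05 = 0.05. Two things follow:
- It could meet the entry score without any contribution from seborrheic dermatitis.
- It would keep the score above 0, the value section 12 gives to no involvement, even if the seborrheic dermatitis had cleared. This assumes that clearance is read from the score; section 14 does not define it.

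No section tells graders how to attribute a lesion to one disease or the other.

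**3. Size per subject.**
One subject is 1/12 = 8.3% of the pairs. If k subjects cannot clear on either side, the highest attainable clearance rate per side is (12 − k)/12: 11/12 = 91.7% for k = 1 and 10/12 = 83.3% for k = 2.

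**4. Illustration of dilution (assumed effect size and k).**
A two-sided paired t-test with n = 12 and alpha 0.05 has 80% power at a standardized mean difference of 0.89 (noncentral t, 11 degrees of freedom). Suppose k subjects have no mean side difference because the second disease drives both sides. The mean effect is then multiplied by (12 − k)/12. Simulated power:

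| k | Mean effect retained | Power, ordinary noise in the k pairs | Power, difference exactly 0 in the k pairs |
|---|---|---|---|
| 0 | 100% | 80% | 80% |
| 1 | 92% | 71% | 75% |
| 2 | 83% | 60% | 70% |
| 3 | 75% | 50% | 64% |

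**5. Illustration of frequency (assumed prevalence).**
If a proportion p of entrants had such a disease, the chance of at least one among 12 is 1 − (1 − p)^12. This is 22% for p = 2%, 46% for p = 5% and 72% for p = 10%. None of these proportions is in the documents.

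**The case against.** **Eligibility may be meant to apply after the wash-out.** Section 6 has topical users wait before enrolling. A subject then off treatment could be called untreated and excluded. This reading is possible and would close the gap, but the protocol does not state it, and section 32 places the two-week run-in after consent.

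**There are other filters.** Wash-out needs the prescribing physician's advice, subjects are to be healthy, and section 16 allows withdrawal when other topical medication is needed. These lower the number of such cases but do not reliably prevent them. *Healthy* is undefined, whoever enters on the prescriber's advice has stopped the drug, and withdrawal is optional and triggered by a need for medication rather than by a flare.

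**Stronger readings that the documents do not support.**
- *Asymmetry in the second disease would pass for an effect of PDT.* A reader might infer bias, but side is randomized and assessors are blinded, so asymmetry is as likely to favour the control side. It adds noise and chance imbalance.
- *Graders cannot tell the diseases apart.* No section says so. Borrowing psoriasis definitions concerns grades of severity, not diagnosis. What can be said is that no attribution rule is stated.
- *A flare costs the pair.* Section 16 says only that subjects may be withdrawn and that data collection then stops, while section 14 includes all participants by intent to treat.
- *A capped clearance rate is a loss in the planned test.* The planned comparison is within the individual. A pair clear on neither side contributes a zero difference, which dilutes the effect.

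**Conclusion.** The concern holds in a limited form. On the text, treated facial psoriasis or atopic dermatitis is admissible, the trial then stops its facial treatment, and the timing of the *untreated* judgement is not stated. That a second disease returns is a possibility, and the documents give no frequency for it.

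If it happens, there are four consequences:
- dilution of, and noise in, the split-face difference;
- clearances of seborrheic dermatitis that cannot be reached or judged;
- possible misattribution, where PDT acts on the other disease and the change is credited to seborrheic dermatitis;
- exposure of the before/after comparisons, namely the within-treatment comparison in section 14 and the microbiome and sebum objectives in section 4, which lack the protection of a concurrent control side.

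The only size that follows from the documents is 1 of 12 pairs per such subject. The power and prevalence figures rest on an assumed effect size, an assumed number of affected subjects and assumed proportions, and the range includes no affected subject at all. The change is worth making because it is small and protects the meaning of the endpoint.

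**What to change.** In section 6, delete *untreated* where it qualifies inflammatory conditions, and state that another current inflammatory dermatosis of the face is excluded whatever its treatment status. Keep the malignancy wording unchanged. Add that the criterion is confirmed at the pre-treatment visit, after the wash-out and run-in.

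A lighter alternative is a single sentence saying that *untreated* is judged after the wash-out. That settles the timing for facial disease whose only treatment has been stopped. It leaves eligible a subject whose second disease is still treated by a route the wash-out does not clearly cover, so the wider wording is preferable.

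The cost is a short eligibility amendment, one recorded check at a visit already planned, and a few lost candidates. The wider wording would also exclude mild or stable second dermatoses, and the number lost cannot be estimated from the documents. The staffing and resources text that follows section 23 calls the recruitment pool sufficient, although that was written under the present criteria.

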**7) Study-Wide Number of Subjects**

12

**8) Study-Wide Recruitment Methods**

Patients will be recruited from the outpatient dermatology clinics in the department of Dermatology at UC Davis. We also recruit participants who live within a 100 mile radius of the dermatology clinics in Sacramento. They will be reassured that their participation or non- participation in the study will not affect the level of clinical care received.

Recruitment flyers are attached.

**9) Compensation to the Subjects**

At the end of visit two, the patient will be paid \$40 for completing visits one and two. If the patient does not follow up for visit 2, they will receive no compensation. At the end of visit three, the patient will be paid an additional \$20 for completing

PROTOCOL TITLE: Pilot study for the use of photodynamic therapy in the treatment of seborrheic dermatitis

visit three. We will make the payments using gift cards.

## **10) Study Timelines**

PROTOCOL TITLE: Pilot study for the use of photodynamic therapy in the treatment of seborrheic dermatitis

The research subject will require 4 visits that are spaced 2-10 weeks apart as outlined in the attached protocol. Each visit will take a total of 1.5 hours. We estimate that each subject will participate for a total of 3-4.5 months from initiation of enrollment to completion of the study.

## **11) Study Endpoints**

The primary endpoint of the study is recruitment of a sufficient number of patients (12) who complete two treatments of photodynamic therapy to the face with grading of the severity of seborrheic dermatitis before each treatment and after each follow-up period.

The secondary endpoints for the study are obtaining swabs for microbiome analysis and facial sebum production rates before each treatment and after each follow-up period.

## **12) Procedures Involved**

Duration of seborrheic dermatitis, previous treatments for seborrheic dermatitis and patient response to the treatments will be recorded. Facial photography will be done for grading the Seborrhea Area and Severity Index Face (SASI-F). All seborrheic dermatitis patients will be graded using the SASI-F [3]. This score is a composite score as follows: the area index, also known as the relative area of facial involvement, is denoted as a fraction of 1 with the normal hairline defining the boundaries of the face. Erythema and scale are separately scored on a 5-point scale using the definitions used to conduct Psoriasis Area and Severity Index scoring (ie, 0 = none, 1 = slight, 2 = moderate, 3 = striking, and 4 = exceptionally striking).

The scores for erythema and scale are then summed and multiplied by the relative area of facial involvement ratio. The maximal score is 8 whereas no involvement would have a score of 0. The inclusion criteria will be similar to the previous trial that used the SASI-F in their analysis [3]. This study will consist of subjects with an erythema score of at least one with the presence of at an area index of 5% or more.

This study will be a single blinded, randomized, intra-individual comparison study consisting of a total of 12 subjects. Patients will be randomized by utilizing an online randomizer. A power analysis is not truly applicable because this is a pilot study that utilizes a potential treatment for seborrheic dermatitis that has not been previously investigated. We plan to recruit up to 12 patients. The treatment will consist of split-face comparisons of no application of aminolevulinic acid (ALA) vs ALA application to either half of the face. Prior to ALA application, the face will be swabbed for microbiome analysis. A schematic for the split-face study is shown in Figure 1. After the ALA application, the subjects will incubate with the ALA on their face per the standard PDT protocol used at UC Davis Dermatology clinic for facial PDT treatments. The side of the face being treated will remain the same during all treatments. The investigator applying the ALA to the patient will be aware of which side is receiving treatment and which side is not, but the patient will be blinded. For the placebo, Demo Levulan Kerastick, which contains no active ingredient and is enclosed in same cardboard sleeve and cap, will be applied to the other side of the face to mimic the surface of the ALA application stick.

PROTOCOL TITLE: Pilot study for the use of photodynamic therapy in the treatment of seborrheic dermatitis

After the ALA incubation is completed, the subjects will be exposed to a treatment dose of blue light from a Blu-U unit per UC Davis Dermatology clinic protocol for PDT treatments.

Calibrated facial pictures will be used for blind grading utilizing the SASI-F scoring system.

A flow diagram of the protocol is shown in Figure 2. The topical ALA used for this study will be Levulan® Kerasticks (DUSA Pharmaceuticals, Inc.). Facial sebum production rate will be measured with SebuMeter®. The swabbing for the microbiome will be performed as non-invasive swabbing from the face that will not cause the patient any pain or discomfort. For the blue light treatment, the total light dose to the face will be consistent with the currently used standard facial exposure PDT protocols at UC Davis.

After the third visit, patients have the option of being seen in the regular dermatology clinics. Based on the disease severity, a treatment modality will then be selected and administered for the untreated side of the face.

The Levulan Kerasticks and Demo Levulan Kerasticks are stored at the Investigational Drug Services (IDS), a Division of the Pharmacy Department at the University of California, Davis. IDS dispenses the Kerasticks upon the investigators' request.

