## **16) Withdrawal of Subjects**

Subjects may be withdrawn without their consent if they acquire any medical issues during the study period which require the use of any other topical medications, oral or parenteral steroids, oral or parenteral antibiotics. They may also be withdrawn if they are found to have any abnormal sensitivity/allergy to the ALA.

If a subject is to be withdrawn without their consent, they will be contacted and the reason(s) for their withdrawal will be explained in full. No further data will be collected from the subject.

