**27) Local Number of Subjects**

A total of 12 subjects will be recruited.

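### Section 11 sets the primary endpoint at 12 completers while sections 12 and 14 recruit at most 12, so it can be met only with full retention to the last required grading

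*Combined protocol and SAP*

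**What the plan says.** Section 11 (Study Endpoints) defines the primary endpoint as "recruitment of a sufficient number of patients (12) who complete two treatments of photodynamic therapy to the face". To count, a patient must also have "grading of the severity of seborrheic dermatitis before each treatment and after each follow-up period". The 12 is therefore a number of completers with full grading, not a number of starters.

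Sections 12 (Procedures Involved) and 14 (Data Management) both state "We plan to recruit up to 12 patients", which is a ceiling. Section 12 also describes a "randomized, intra-individual comparison study consisting of a total of 12 subjects", and section 14 repeats the total. Section 7 gives the study-wide number as 12, and section 27 says "A total of 12 subjects will be recruited".

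Losses are foreseen. Section 16 says "Subjects may be withdrawn without their consent if they acquire any medical issues during the study period" where these call for certain other medications, and it also allows withdrawal for ALA sensitivity. After withdrawal without consent, "No further data will be collected from the subject". Section 9 provides for patients who do not return for visit 2. Section 10 expects four visits over 3 to 4.5 months.

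Section 14 names a different primary endpoint, complete clearance compared within patients by a two-sided paired t-test, and includes all participants by intention to treat.

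**The concern.** The number that must complete equals the largest number that may start, so the plan leaves no room for a single early loss. Because the recruitment figure is an upper limit, fewer than 12 could also start, and the endpoint would then be out of reach from the outset.

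The grounds for withdrawal are not remote. Section 15 foresees treating secondary infection with antibiotics and local inflammation with topical steroids. These overlap with the medication classes that section 16 lists as grounds for withdrawal, so a treatment reaction could itself remove a completer.

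What is at stake is how the pilot's feasibility result is read. With 11 of 12 completing (92%), retention would be good, yet the primary endpoint in section 11 would not have been reached. The team would then have to decide after the fact whether 11 is enough.

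**Working it through.** **Inputs from the documents**
- Completers required: 12 (section 11).
- Maximum recruited: 12 (sections 12 and 14).
- Dropout rate, replacement rule, over-recruitment, threshold below 12: none in the available text.
- Power, effect size, SD: none. Section 12 says that a power analysis does not apply to this pilot, so no sample-size formula can be reproduced.

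**Step 1: consistency of the two figures.** To expect 12 completers at dropout rate q, recruitment must be 12/(1 − q). This equals 12 only at q = 0. The stated pair of numbers is consistent only if nobody is lost.

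**Step 2: slack.** Maximum completers after w relevant losses = 12 − w. With w = 1 this is 11, below 12. A relevant loss is one before the second treatment or before the last required grading. A subject lost after that grading still counts.

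**Step 3: chance of meeting the endpoint.** Assume that 12 subjects start and that losses are independent with probability q each. Then P(all 12 complete) = (1 − q)^12. The documents give no q, so a range is shown. The last two columns are binomial tail probabilities with n = 12 and completion probability 1 − q. They show how sharply the answer depends on requiring all 12.

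| Assumed q | All 12 complete | At least 10 of 12 | At least 9 of 12 |
|---|---|---|---|
| 5% | 0.95^12 = 54% | 98% | 99.8% |
| 10% | 0.90^12 = 28% | 89% | 97% |
| 15% | 0.85^12 = 14% | 74% | 91% |
| 20% | 0.80^12 = 7% | 56% | 79% |

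**Step 4: retention needed.** For an 80% chance that all 12 complete, q must be at most 1 − 0.8^(1/12) = 0.018, about 1.8% per subject.

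**Step 5: what 12 subjects can show about completion.** The exact 95% confidence interval is 74% to 100% for 12 of 12 and 52% to 98% for 10 of 12. Even perfect retention leaves wide uncertainty, so an estimate with its interval is more informative than a single required count.

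**The case against.** The strongest reply is that section 11 is a loosely worded recruitment goal for a small pilot. It sets no test and no stated consequence if 11 complete, and the objectives in section 4 concern efficacy, microbiome and sebum rather than feasibility. That limits the consequence. It does not remove the mismatch, because section 11 calls this the primary endpoint and puts a number on it.

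Several stronger readings are tempting, and the documents do not support them:

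- *The efficacy analysis fails with 11 subjects.* It does not. The paired comparison in section 14 can be run on fewer pairs, and since no power target exists, no planned power is lost.
- *Any withdrawal defeats the endpoint.* Only one before the second treatment or the last required grading does.
- *Section 27 also caps recruitment.* Its wording is a target. Only sections 12 and 14 set an upper limit.
- *Replacement is ruled out.* The available text gives no replacement rule. Section 10 refers to an attached protocol, and the figures are not shown, so a rule there cannot be excluded.
- *The endpoint will probably be missed.* The probabilities are illustrations at assumed rates, not evidence about retention in this trial.

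It may also be said that the intention-to-treat statement in section 14 covers losses. It governs who is analysed and cannot turn a non-completer into a completer.

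**Conclusion.** The point holds in a limited form. The section 11 endpoint requires every one of at most 12 recruits to reach the last required grading, and the available text provides no margin although it foresees losses. The zero margin follows from the stated numbers without any assumption. Its practical size depends on a dropout rate that the plan does not give: over an assumed 5% to 20% with independent losses and a full 12 starting, the chance of meeting the endpoint falls from 54% to 7%.

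What fails is the section 11 endpoint as worded, not the study. A reader might infer that the trial as a whole would be invalid at 11 completers. Section 14 does not support that, because its own primary endpoint is complete clearance and does not require 12 completers. The existence of two different primary endpoints is a reason to settle both in one edit.

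**What to change.** Keep 12 as the number enrolled and stop describing it as the number of completers. Restate the feasibility endpoint in section 11 as the number and proportion of enrolled subjects who complete both treatments and all required gradings, with an exact 95% confidence interval. If a success threshold is wanted, the sponsor should set it before enrolment, as a proportion of those enrolled and below 100%. A proportion stays defined if fewer than 12 enrol, whereas a fixed count out of 12 does not. The documents give no basis for any particular value, so that choice is the sponsor's.

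In the same edit, reconcile section 11 with section 14 so that one primary endpoint is named and the other is given a secondary role.

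The cost is a short revision of sections 11 and 14, with no added subjects or procedures. The completer figure on paper becomes slightly less favourable.

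If 12 completers are truly wanted, a replacement rule or a higher ceiling would also resolve the mismatch, but at the price of more enrolment. Using 12/(1 − q), rounded up, this means 13, 14, 15 or 15 recruits at assumed losses of 5%, 10%, 15% or 20%. For at least a 90% chance of 12 completers, it means 14, 15, 16 or 18.
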